14.0 Withdrawal of Subjects

The PI does not anticipate having to a) withdraw subjects from this research without their consent or b) terminate the study early.^{46,47}

As described previously, the consent form will remind participants of the food tasting and rating task that will take place during the lab visit. Participants will be

PROTOCOL TITLE: Decision Making Study

instructed to alert a member of the study team if they have a relevant food allergy. If this occurs, the participant will be informed that they do not meet the eligibility criteria for the study and thus will not be scheduled for the lab visit (i.e., they will be withdrawn from the study for not meeting eligibility criteria).

If a participant arrives at the lab and does not appear to meet the minimum BMI criteria ($BMI = 30 \text{ kg/m}^2$), the research assistant will be instructed to re-assess eligibility criteria to catch errors that were possibly made on the screening survey when reporting height and weight. Participants who may have entered inaccurate height or weight information on the screening survey (and thus do not meet the required BMI cutoff) will be told they cannot enroll in the study as they do not meet eligibility criteria. We do not anticipate having to do this very often, but it has happened a few times in our previous work, so we will have a procedure in place to address it.

Participants may decide to withdraw from the study at any time. No additional data will be collected after a participant withdraws. If a participant shares their intent to withdraw, the investigator will ask if the information that has already collected can be used or whether it should be destroyed.

15.0 Risks to Subjects

Potential Risks: Participants may experience psychological distress in response to the experimental manipulation. The manipulation used in this study is like other commonly used procedures designed to produce acute short-term distress in a laboratory setting^{49,50,114-119} without affecting long-term mental or physical health. Distress is expected to be no stronger than what participants might experience in response to a single instance of day-to-day weight discrimination outside the lab. These risks are considered to be minimal as both the probability and magnitude of discomfort are not anticipated to be greater than those ordinarily encountered in daily life. It is also important to note that the negative effects of weight discrimination on health are presumed to be cumulative over the life course and develop only after repeated exposure to the chronic stress of weight discrimination experienced over time. Our manipulations simulate a single instance of weight-based discrimination and thus should have measurable acute effects in the lab without contributing to long-term risk.

Potential risks also include those associated with providing the three saliva samples (e.g., disgust with the procedure, difficulty producing enough saliva). Overall, these risks are considered to be minimal as the probability and magnitude of harm or discomfort anticipated in this study are not greater than those ordinarily encountered in daily life.

Information about the study's actual purpose will be withheld from participants until the debriefing process, which will take place at the end of the lab-portion of the study. During the consent process the experimenter will provide participants with a statement to the effect that participants may not be made aware of some features about the study and will be provided with additional information about the study at the end of their participation or at any time they withdraw. All participants will take part in the funneled debriefing process at the end of their participation or at any time they withdraw. Please

PROTOCOL TITLE: Decision Making Study

see attached for the full text of the verbal debriefing script and the written debriefing form.

16.0 Potential Benefits to Subjects

Potential benefits of the research for participants are minimal. Participants will learn (via debriefing) about the potential negative effects of weight discrimination on health and will be provided with links to several readings if they are interested in learning more about it.

17.0 Data Management and Confidentiality

Statistical Design, Power, and Analysis Plan

We designed this study to have very high power for the main effects of weight discrimination (Aim 1) and to ensure sufficient sensitivity for moderation effects of psychological (Aim 2) and demographic variables (Aim 3).

➤ **Aim 1: Identify early-stage cognitive, affective, behavioral, and physiological mechanisms activated by experimentally manipulated weight discrimination.** We hypothesize that, relative to participants in the control condition(s), participants in the weight discrimination (experimental) condition (vs. control) will display more impaired self-regulation, higher negative emotion, lower positive emotion, more social withdrawal and comfort eating, lower self-efficacy and intentions for engaging in weight control behavior, and increased cortisol secretion.

Aim 1 power and analysis. Nine outcomes are assessed for the study (Table 1), hence we adopt a conservative Bonferroni adjustment when evaluating the primary hypothesis and use significance level $\alpha = 0.005$ to maintain familywise Type I error rate of 0.05. We assumed conservative effect size estimates, which were among the smallest observed in our pilot data.⁴⁸ We plan to recruit 160 subjects per condition for the study, which yields 90% power ($\alpha = 0.005$) to detect the medium Cohen's $d = 0.50$ between the control and experimental conditions.

Aim 1 analyses will use unadjusted ANOVA followed by analysis of covariance and multiple regression methods that permit adjustment for age and other baseline characteristics that may exhibit imbalance across experimental conditions. To analyze effects of the manipulation on cortisol secretion (assessed at 3 timepoints), we will calculate the area under the curve (AUC) with respect to ground (AUCg).¹²⁰ For all Aims, residual diagnostics will assess model assumptions (e.g., normality, homogeneity) and responses will be transformed if necessary. Effect of experimental weight discrimination will be reported for both unadjusted and adjusted analyses.

➤ **Aim 2: Identify psychological variables that moderate effects of weight discrimination.** We hypothesize that the effect of weight discrimination (vs. control) will be stronger for individuals who score higher on certain psychological variables (i.e., internalized weight bias, neuroticism) and weaker for individuals who score higher on other variables (i.e., self-compassion, conscientiousness; See Table 2). In other words, possessing some traits will be protective, while possessing other traits may render individuals more vulnerable to the harmful effects of weight discrimination.

Aim 2 power and analysis. The very high power of these designs for the primary hypotheses of Aim 1 ensures sufficient power for Aim 2 and additional analyses.

PROTOCOL TITLE: Decision Making Study

Statistical analysis will use multiple regression with condition assignment, the moderator, and their interaction as predictors and focus on interpretation of the coefficient for the interaction.¹²¹ With a continuous moderator, the coefficient for the interaction is the difference in the slope coefficients associated with the moderator in each of the treatment groups. Because these slopes are proportional to the correlation between the moderator and outcome in each group, respectively, the test of no moderation is equivalent to the test of equal correlation between moderator and outcome in all groups. Using Fisher's z transform of the correlations to approximate normality, The study (with 160 subjects in each of two conditions) provides 90% [80%] power (2-sided, $\alpha = 0.05$) to detect the change in correlation between moderator and outcome from 0.65 to 0.39 [0.43] associated with treatment assignment.¹²² Additional statistical analyses will adjust for baseline characteristics by including these as additional predictors in the model; estimated moderation effects will be reported for both unadjusted and adjusted analyses.

➤ **Aim 3: Identify demographic characteristics that moderate effects of weight discrimination.** We will conduct exploratory analyses to assess whether the negative effects of weight discrimination are moderated by age, sex/gender, race, and ethnicity.

Aim 3 power and analysis. The power to detect a moderating effect of age is similar to continuous moderators described in Aim 2. Defining the effect of a binary moderator as the difference in the standardized effects of intervention associated with the two levels of the moderator, The study provides 88% power for a moderator effect of 0.70.¹²² If the moderator is unbalanced (e.g., 60% of participants are female), then the power to detect a moderator effect of 0.70 is 86%. Power is maintained at 84% when there is a more severe imbalance (e.g., 1/3 Hispanic vs. 2/3 non-Hispanic).

All analyses will use the intent-to-treat data sets, meaning all participants will be included and associated with the experimental condition to which they were assigned. Missing outcomes will be addressed using multiple imputation or marginalization (i.e., maximum likelihood). Based on our pilot work, we anticipate little missing data. If the missingness exceeds 10%, however, we will evaluate the potential for nonignorability by including indicators for missingness throughout our analyses.

Participant privacy and data will be carefully protected. Participant information will be collected using a secure web-based application. The baseline survey will be as brief as possible and will be configured for easy completion on multiple platforms (e.g., cell phone, tablet, laptop). Participants will have the option to skip questions that make them uncomfortable. The experimental session will take place in a private laboratory on campus and will be guided through the study by a research assistant.

Data Security

Procedures to eliminate risks related to breach of confidentiality are as follows: Each participant will be given a unique identifier in the data set which will be stripped of all personal information to protect confidentiality. Data sets used for analysis will contain participant identification numbers but neither names nor any other identifying information. Identification information will be retained by the PI for the duration of the study and stored separately from the responses provided by subjects. Data will be stored in password-protected databases on secure servers, accessible only to project staff. Collaborators will receive data stripped of personal identifiers (de-identified data). To ensure complete confidentiality, access to the “key” linking personal identifiers to

PROTOCOL TITLE: Decision Making Study

participant usernames and passwords will be restricted to the PI. [name] will oversee the data storage and reporting procedures. The “key” linking personally identifiable information to the participant’s ID in the data set will be destroyed at the end of the study. Reports will only use aggregated data and will not identify individual participants. All study staff will be trained in security and confidentiality procedures before receiving access to any participant data.

Quality Control

The baseline and lab-based survey will include several data quality checks (e.g., attention checks) and a “speeding check” to identify any surveys that may be associated with poor quality.

Data Handling and Storage

All data will be stored on the PI’s password protected computer in a secure folder on the College of Medicine server. [name] will oversee data storage and handling procedures. Only members of the study team will have access to the data. De-identified data will be stored into perpetuity. Collaborators will receive data stripped of personal identifiers (de-identified data). Data transmission procedures will follow best practices to ensure data safety and security during transfer.

Saliva samples will be handled following standard laboratory procedures to ensure participant privacy and specimen protection. Saliva samples will be frozen at -20°C within 2 hours of collection and will be stored in a secure area (card-access only). Saliva samples will be stored until they are ready for analysis. Samples will be assayed for cortisol by an outside laboratory in small batches or once data collection is complete, depending on how quickly data collection takes place. Specimens will be shipped following standard protocols required by the processing lab.

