12.0 Local Number of Subjects

Total number of subjects: 320

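### The Aim 1 power statement does not follow from its own inputs (about 95%, not 90%), and the fixed 0.005 threshold is a rounded-down Bonferroni value that Holm's procedure would improve on

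*Combined protocol and SAP*

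**What the plan says.** All of this stands in section 17.0, under the power and analysis text for Aim 1, unless noted.

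- **Number of tests and method:** "Nine outcomes are assessed for the study (Table 1), hence we adopt a conservative Bonferroni adjustment when evaluating the primary hypothesis". Table 1 in section 3.0 does list nine: Stroop, delay discounting, negative emotion, positive emotion, social withdrawal, self-efficacy, intentions, comfort eating and cortisol.
- **Threshold:** "use significance level $\alpha = 0.005$ to maintain familywise Type I error rate of 0.05".
- **Sample size:** "We plan to recruit 160 subjects per condition for the study". Section 12.0 agrees: "Total number of subjects: 320".
- **Power:** the sample size is one "which yields 90% power ($\alpha = 0.005$) to detect the medium Cohen's $d = 0.50$ between the control and experimental conditions".
- **Sidedness:** not stated for Aim 1. The Aim 2 statement specifies "power (2-sided, $\alpha = 0.05$) to detect the change in correlation between moderator and outcome".
- **Loss:** the power statement contains no allowance. Later in section 17.0 the plan expects little missing data and names only a 10% level, above which it would examine nonignorable missingness.

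No stepwise multiplicity procedure is named.

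**The concern.** Three numbers that should fit together (the threshold, the sample size and the power for the primary aim) do not. Either the power figure is wrong or an input behind it, such as a loss allowance, was left out. A reader cannot tell which. The Aim 2 text then leans on the high power claimed for Aim 1.

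The threshold has a smaller problem. A p-value between 0.0050 and 0.0056 would pass the Bonferroni rule for nine outcomes but fail the stated cut-off, and the plan does not say that it rounded down.

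Single-step Bonferroni also matters here because the plan predicts an effect on every one of the nine outcomes. That is the situation in which a step-down method recovers most power for the same familywise error.

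**Working it through.** **Inputs.** From section 17.0: n = 160 per arm, d = 0.50, α = 0.005, nine tests, familywise 0.05, and unadjusted two-group ANOVA (equivalent to a two-sample t-test). Assumed: two-sided testing as in Aim 2, all 160 per arm analysed, and a continuous outcome.

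**1. The plan's power figure.**

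Normal approximation: power = Φ(d·√(n/2) − z₁₋α/₂).
- d·√(n/2) = 0.50 × √80 = 4.472
- z₀.₉₉₇₅ = 2.807
- power = Φ(4.472 − 2.807) = Φ(1.665) = 95.2%

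The exact noncentral t gives 94.9%. The stated 90% is not reproduced. A one-sided test moves further away, to about 97%.

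**2. What would give 90%?**

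| Change to the inputs | Result |
|---|---|
| Keep d = 0.50 and solve n = 2(2.807 + 1.282)²/0.50² | 134 per arm (z), 136 per arm (t) |
| Keep 160 per arm and solve for d | d = 0.46 |
| 136 analysed per arm, a loss of 1 − 136/160 = 15% | 90.1% |
| 10% missing, 144 analysed per arm | 92.0% |

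Only an unstated loss of about 15% gives 90% at d = 0.50.

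**3. The threshold.**

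- Bonferroni for nine tests: 0.05/9 = 0.00556. The stated 0.005 equals 0.05/10.
- Familywise bound at 0.005: 9 × 0.005 = 0.045. If the tests were independent: 1 − 0.995⁹ = 0.0441.
- Power at d = 0.50 (t) moves from 94.9% at 0.005 to 95.3% at 0.00556.

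The 0.05 limit is kept, and the correction alone gains less than half a percentage point.

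**4. Holm against the fixed 0.005.** Simulation with 100,000 draws, nine normal test statistics, 160 per arm, two-sided. The correlation of 0.3 is an assumption, as the documents give none. Mean power per true effect at the plan's d = 0.50:

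| Real effects | Fixed 0.005 | Holm at 0.05 |
|---|---|---|
| 9 of 9 | 95.2% | 99.1% |
| 5 of 9 | 95.1% | 96.9% |
| 1 of 9 | 95.2% | 95.6% |

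No draw had a rejection at 0.005 that Holm missed. Familywise error with no real effects was 4.1% at 0.005 and 4.6% with Holm.

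For sensitivity only, at an assumed d = 0.35 and the same correlation, mean power goes from 63% to 76% (nine real), 63% to 68% (five) and 63% to 64% (one).

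**The case against.** The strongest reply is that nothing here endangers the trial. The plan calls its adjustment conservative. It undertakes only "to maintain familywise Type I error rate of 0.05", and 0.045 does that. The power error is in the safe direction: the sample exceeds the roughly 136 per arm needed for the stated target, and correcting the figure strengthens the claim of high power. Single-step Bonferroni is valid and prespecified, so Holm is an improvement and not the repair of an error. All of this stands.

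Three stronger readings are tempting, and the documents do not support them.

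- **That 0.005 is a wrong alpha that breaks error control.** It is stricter than necessary, and the familywise limit holds.
- **That Holm would transform the trial.** The larger gains need d = 0.35, which is not in the plan. The plan's value is d = 0.50, which it describes as conservative and among the smallest effects in its pilot data. At that value the gain per outcome is modest, and nearly nil if only one effect is real. Detecting all nine outcomes is not a success criterion in the plan.
- **That Holm costs nothing.** It never rejects less, but simultaneous confidence intervals that match its decisions are less direct than Bonferroni intervals, and each outcome's threshold depends on the other eight p-values.

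The reply does not rescue the 90%. No stated input, and neither choice of sidedness, produces it.

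**Conclusion.** The power statement for the primary aim is wrong as written, or is missing an input. At the stated values power is about 95%, an understatement of about five points. This rests on two-sided testing, full data on 160 per arm and a continuous outcome. It does not carry over directly to social withdrawal, which section 6.0 records as a choice among three options.

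The 0.005 threshold is a small, safe imprecision. It is consistent with deliberate rounding down, and type I error is controlled. No change in sample size follows.

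Holm is a worthwhile, nearly free improvement. How much it gains depends on how many of the nine effects are real and on the assumed correlation.

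**What to change.** 1. Restate Aim 1 power as about 95% for d = 0.50, or 90% for d = 0.46, with 160 per arm at two-sided 0.005. At Holm's first step (0.0056) the d = 0.50 figure is 95.3%. If 90% was meant to include losses, state the allowance; about 15% gives that figure.
2. State that Aim 1 tests are two-sided, if that is intended.
3. Replace the fixed 0.005 with Holm's step-down procedure over the nine Table 1 outcomes at familywise 0.05, with the first step at 0.05/9 = 0.0056, and say how confidence intervals will be reported alongside it.
4. If Bonferroni is kept, say that 0.005 is 0.0056 rounded down.

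The cost is SAP wording, settled before anyone sees outcomes by condition. No extra participants or data are needed. The only trade-off is the less direct simultaneous intervals.

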Social withdrawal. Social withdrawal will be assessed with a measure from previous research,⁵⁰ in which participants indicate the extent to which they want to work on a task either by themselves, with one of their former group members, or with a new partner. Choosing to work by oneself reflects a desire to avoid social interaction. The details of the task will be tailored for the study to fit the study's narrative flow.

Comfort eating. Comfort eating will be assessed via an eating task to objectively measure hyperpalatable (high-fat, -sodium, -sugar, and -carbohydrate) food intake.¹⁰¹ To avoid floor effects often observed in laboratory eating settings, the eating task will take place under the guise of a faux taste test.¹⁰² Participants will be asked to rate each of the

PROTOCOL TITLE: Decision Making Study

foods/drinks to ostensibly guide the development of their food marketing campaign later during the study. To avoid ceiling effects and to allow participants to eat without fearing that the experimenter will negatively judge the amount they have eaten, large quantities of each food will be made available. Participants will have 10 minutes to complete the task alone in a private room. Bowls will be weighed (unobtrusively) before and after the task to compute the difference in grams, which will then be converted to kilocalories based on published nutrition information from the food maker.

Self-efficacy for weight control behavior. Self-efficacy (perceived confidence) in one's ability to engage in weight control behaviors (e.g., dietary restraint, physical activity) over the next six months will be assessed with items adapted from previous research. Self-efficacy for dietary restraint will be assessed with the short form of the Weight Efficacy Lifestyle Questionnaire¹⁰³ (e.g., I can resist eating ... when I am depressed or down; 8 items). Self-efficacy for physical activity will be assessed with the Exercise Self-efficacy Scale¹⁰⁴ (e.g., I am confident I can participate in regular exercise when ... I am tired; 5 items). To mask the study's focus, weight control items will be interspersed with items assessing self-efficacy for other health behaviors (e.g., flu vaccination, sleep, cancer screening). Participants will rate their self-efficacy for each behavior on an 8-point scale (0=not at all confident to 7=very confident). Items will be averaged to create a composite score.

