Debriefing Procedure Summary: The research assistant will begin by asking the participant a series of questions to assess prior knowledge of any aspects of the study (e.g., “Did anyone else tell you anything about what you would be doing in this study before your session today?”) and gauge suspicion about study procedures (e.g., What do you think today’s study was about? Was there anything we told you during the study that you didn’t believe?”). Afterwards, the research assistant will explain the goals of the study and the nature of the two experimental conditions. All aspects of the procedure, including all elements of deception, will be explained clearly to participants. Participants will be assured that any feedback they received during the session from their ostensible partners was not real (i.e., the GTKY and first impression ratings from their “co-workers,” being told that no one wanted to work with them on the partner task) and was developed by the research team to elicit particular types of reactions. Research assistants will emphasize this point until they are confident participants understand that none of the study procedures reflect any actual evaluation of the participant. The research assistant will apologize for not initially disclosing the purpose of the study and apologize for any discomfort that may have been experienced while completing the study measures or tasks.

Research assistants will be trained on how to assist participants who experience distress. Further, participants will be given a list of psychological support resources they can utilize (e.g., helplines) if they experience any lingering distress after the study has ended. Upon receiving full disclosure of the study goals, participants will be given the opportunity to withdraw their data from the study.

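### Aim 1 power is misstated: 160 per condition at alpha 0.005 gives about 95% power for d = 0.50, not 90%

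*Combined protocol and SAP*

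**What the plan says.** Section 17.0, under Aim 1 power and analysis, divides the 5% familywise error across nine outcomes and tests each at alpha 0.005. It then says: "We plan to recruit 160 subjects per condition for the study, which yields 90% power", for a Cohen's d of 0.50. The planned test is an unadjusted ANOVA of two conditions, followed by covariate-adjusted models. The Aim 1 text does not say whether the test is one- or two-sided.

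The same section gives power for the other two aims.

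- **Aim 2:** "The study (with 160 subjects in each of two conditions) provides 90% [80%] power (2-sided", alpha 0.05) for a change in correlation from 0.65 to 0.39 [0.43].
- **Aim 3:** "The study provides 88% power for a moderator effect of 0.70", falling to 86% with a 60/40 split of the moderator. For a one-third/two-thirds split, "Power is maintained at 84% when there is a more severe imbalance". Neither alpha nor sides are given for Aim 3.

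On the analysis set, the section says: "All analyses will use the intent-to-treat data sets, meaning all participants will be included". On missing data: "Based on our pilot work, we anticipate little missing data". Section 6.0 adds that after debriefing "participants will be given the opportunity to withdraw their data from the study", with no expected rate.

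**The concern.** The Aim 1 sentence supplies the sample size, alpha and effect size, so its power can be recomputed directly, and the result is about five points higher than stated. Put as type II error, the plan states 10% where its inputs give about 5%.

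The difference does not threaten the trial, because the stated figure is too low rather than too high. What is lost is the meaning of the number. A reader cannot tell whether 90% power refers to d = 0.50 after an unstated loss of participants or to a smaller effect, d = 0.46, with complete data. These are different claims about sensitivity, and the distinction matters when null results among the nine outcomes are interpreted. The Aim 2 paragraph also argues from the high power of Aim 1, so the Aim 1 figure should be right.

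**Working it through.** **Inputs, all from section 17.0.** n = 160 per condition, equal allocation; d = 0.50; alpha = 0.005; two-group ANOVA. Two-sided testing is assumed, because a two-group F test is equivalent to a two-sided t test and Aim 2 is labelled 2-sided. One-sided results are shown as well.

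**Step 1: the stated 90%.** The noncentrality is d × √(n/2) = 0.50 × √80 = 4.472, on 2 × 160 − 2 = 318 degrees of freedom. The two-sided critical value at 0.005 is 2.827. Power from the noncentral t distribution is 94.9%. A normal approximation, Φ(4.472 − 2.807), gives 95.2%.

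| Reading of alpha | Power, n = 160, d = 0.50 |
|---|---|
| Two-sided 0.005 | 94.9% |
| Two-sided 0.05/9 = 0.00556 | 95.3% |
| One-sided 0.005 | 96.9% |
| Two-sided 0.0025 (alpha halved again) | 92.2% |

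None of these is 90%.

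**Step 2: what would give 90%.** With all 160 per condition, 90% is reached at d = 0.46 two-sided (80% at d = 0.41), or at d = 0.43 one-sided. Holding d = 0.50, two-sided power falls with the number analysed:

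| Analysed per condition | Loss from 160 | Power |
|---|---|---|
| 160 | 0% | 94.9% |
| 152 | 5% | 93.6% |
| 144 | 10% | 92.0% |
| 136 | 15% | 90.1% |
| 135 | 15.6% | 89.8% |

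So 136 is the smallest number analysed that gives 90% two-sided. One-sided it is 121, a loss of 24%.

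**Step 3: do the other power figures assume a loss?** The same check was made at 160 and at 136 per condition.

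- *Aim 2*, Fisher z, standard error √(2/(n − 3)), two-sided 0.05 as stated. For 0.65 against 0.39 the difference in z is 0.7753 − 0.4118 = 0.3635. At n = 160 the standard error is 0.1129, the ratio is 3.221, and power is Φ(3.221 − 1.960) = 89.6%. For 0.65 against 0.43 the difference is 0.3154, the ratio 2.794, and power 79.8%.
- *Aim 3*, a difference of 0.70 in standardised effects, standard error √(2/(np) + 2/(n(1 − p))), two-sided 0.05 assumed, noncentral t on 2n − 4 degrees of freedom. At n = 160 and p = 1/2 the standard error is 0.2236, the ratio is 3.130 and power is 87.7%.

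| Figure | Stated | At 160 | At 136 |
|---|---|---|---|
| Aim 2, 0.65 to 0.39 | 90% | 89.6% | 84.2% |
| Aim 2, 0.65 to 0.43 | 80% | 79.8% | 73.0% |
| Aim 3, even split | 88% | 87.7% | 82.0% |
| Aim 3, 60/40 split | 86% | 86.4% | 80.4% |
| Aim 3, 1/3 to 2/3 split | 84% | 83.7% | 77.4% |

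All five figures for Aims 2 and 3 round to the stated values at 160, and none does at 136. The Aim 1 figure is the only one that does not follow from 160 per condition.

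**The case against.** The strongest reply is that 160 is described as a recruitment number, and that 90% is what remains after about 15% loss (136 analysed, 90.1%). The protocol does describe routes to loss: withdrawal at any time with possible destruction of data (section 14.0), withdrawal of data after debriefing (section 6.0), insufficient saliva (section 18.0), and foods withheld or the tasting cancelled because of allergy (section 6.0). An allowance of this kind is a plausible origin of the figure.

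It cannot be read into the text, however. No loss rate is given anywhere. Section 17.0 includes all participants and expects few missing values. At its own 10% missingness threshold, power is still 92.0%. If Aim 1 rests on 136, it uses a different sample size from Aims 2 and 3 without saying so.

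A second reply is that 90% was meant as a lower bound. That would be true for any loss up to 15%, but the sentence does not say it.

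Two parts of the reply stand. The error has no consequence for the design. And 95% is a full-data figure, so any correction should say how many participants it assumes are analysed.

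**Conclusion.** The concern holds. The stated 90% does not follow from 160 per condition, d = 0.50 and alpha 0.005. The power is 94.9% two-sided, about five points higher, and 96.9% one-sided. The two-sided figure rests on an assumption about sides that the planned ANOVA supports, and on complete data in both conditions. The error understates power, so 160 per condition remains more than enough for the stated target, and neither alpha nor the analysis needs to change. The point is minor: a wrong figure in the sample-size justification for the primary aim, to be corrected in wording.

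**What to change.** In section 17.0, Aim 1, replace the power statement with one of the following, according to what was intended.

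- *Full data:* 160 per condition analysed gives about 95% power for d = 0.50, and 90% power for d = 0.46, at two-sided alpha 0.005.
- *With a loss allowance:* 160 recruited and 136 analysed per condition (15% loss) gives 90% power for d = 0.50 at two-sided alpha 0.005.

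If the second is chosen, the plan should also say that the Aim 2 and Aim 3 figures assume all 160 per condition, or restate them at 136 (about 84% and 73% for Aim 2; about 82%, 80% and 77% for Aim 3, assuming two-sided 0.05).

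The cost is a sentence or two. No participants, data or analyses are added. The full-data statement presumes no loss: power is 92.0% if 10% of each condition is lost and 90.1% if 15% is lost. The sponsor therefore has to decide which analysed number it is prepared to state.
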